4 STUDY PROCEDURES

4.1 Home Monitoring

Subjects will record their PIFR using the InCheck DIAL® and modified Borg dyspnea score three times weekly (MWF) when clinically stable and daily while respiratory symptoms worsen per patient self-assessment. At each session, the participant will repeat efforts three times, with the highest of the three repeated efforts being recorded by the participant. They will be asked to perform the PIFR for the DPI(s) they are receiving at home (Ellipta®, Inhub®, Diskus® or Handihaler®) using the InCheck DIAL®. If on more than one DPI, patient will record PIFR for each device. PIFR will be recorded with best approximation to nearest 1 L/min.

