- We will use mixed models to explore associations of monthly PIFR averages over time and clinical and demographic factors. Subjects will be considered as random factor, other variables will be considered fixed effects.
- Association of PIFR with CAT score, mBORG score and mMRC
 - Association of PIFR and CAT scores at V1, V3, V4, V5, V6 (for PIFR, use the measurement in the week of each telephone follow-up, or the month average)

- Correlation of change in CAT scores with change in PIFR from baseline after 24 weeks
- Association of PIFR and mBORG score at V2, V3, V4, V5, V6
- Association of PIFR and mMRC scores at V1, V3, V4, V5, V6 (for PIFR, use the measurement in the week of each telephone follow-up, or the month average)

For COPD exacerbation analyses, the proportion of patients with COPD exacerbations (from Kaplan Meier curve) and the rate of exacerbations occurring during follow-up will be reported along with 95% CI. A patient will be considered censored for exacerbations at the time of the last documented visit, the end of the study, the switching of device (between medium and high resistance DPI) or death (whichever occurs earlier), if they did not experience an exacerbation before. The exacerbations will be reported overall and stratified by severity. The associations between exacerbations and PIFR will be explored in different ways, for all exacerbation, stratified by severity of exacerbations, and stratified by device.

- The rate of exacerbations and sPIFR will be analyzed with negative binomial models (or another model if more appropriate).
- For patients with exacerbations, the mean of PIFR in the week before, of, and after each exacerbation will be calculated and reported.

All tests with p value < 0.05 will be interpreted nominally as statistically significant.

Missing data

- No imputation for PIFR
- No imputation for COPD exacerbations
- No imputation for CAT, mBORG and mMRC

Sample Size and Power

In this application, we propose to recruit 120 COPD participants for study enrollment. There are several rationales for this sample size selection.

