7 STUDY PROCEDURES

This is an observational study but certain study procedures and PROs will be measured in the study. Procedures includes performing pre- and post-bronchodilator PIFR as well as completion of PROs during clinic visits. In the home setting, subjects will be expected to record PIFR and modified Borg score three times weekly (MWF), or more often with worsened symptoms.

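### Monthly PIFR averages do not allow for daily reading during worsening, so a plain mean over-weights worsened days and overstates that month's PIFR loss

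*Combined protocol and SAP*

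**What the plan says.** Section 4.1 ties the frequency of home readings to the patient's condition: "three times weekly (MWF) when clinically stable and daily while respiratory symptoms worsen per patient self-assessment". Appendix 1 repeats this. Section 7 agrees on direction but is looser on frequency: "three times weekly (MWF), or more often with worsened symptoms".

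Section 6.3 uses the monthly average as a mixed-model outcome: "We will use mixed models to explore associations of monthly PIFR averages over time and clinical and demographic factors". On model structure it says only "Subjects will be considered as random factor, other variables will be considered fixed effects". For the CAT and mMRC associations it allows two choices: "for PIFR, use the measurement in the week of each telephone follow-up, or the month average". On missing values it says "No imputation for PIFR".

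The plan does not say how a monthly average is formed. It has no weighting, no restriction to the scheduled weekdays and no named model term for clinical state. All these analyses are exploratory, but describing PIFR over time and its predictors is a stated objective (section 2.1), and section 6.3 will read p < 0.05 as nominally significant.

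**The concern.** The number of readings on a given day depends on how the patient feels, and section 1.3 gives reasons to expect PIFR to be lower when the patient feels worse. Sampling frequency is therefore linked to the quantity being averaged. A mean of whatever was recorded is not the patient's mean PIFR over the month; it leans towards the worsened days. A random subject effect does not correct this, because the distortion is already in the outcome before the model is fitted.

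Only months with worsening are affected. A factor that goes with more frequent or longer worsening could therefore show an association with monthly PIFR that partly reflects how often readings were taken. The descriptive means per patient and the optional weekly or monthly summaries in section 6.3 have the same weakness.

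**Working it through.** **The plan's own figure.** There is none for the monthly average or its bias. The sample-size table in section 6.3 does not enter this check.

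**Inputs**
- Stable reading rate: 3 per 7 days (section 4.1).
- Worsened reading rate: 1 per day (section 4.1, Appendix 1).
- Worsened days per month, w: not stated, and left to patient self-assessment. Assumed, with 5 to 14 days shown in detail.
- Month length, M: 28 days (30 gives similar results, below).
- Size of the PIFR fall, D: section 1.3 cites a 17-22% rise between hospital admission and recovery. This is an inpatient figure.
- Stable PIFR: 65 L/min (low-medium resistance) and 38 L/min (high resistance), from the pilot data in section 1.3.

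**Relative size.** The worsened share of days is w/M. The worsened share of readings is w / (w + (M − w) × 3/7). The monthly loss is D times the share, so D cancels from the ratio:

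overstatement = M / (w + (M − w) × 3/7) − 1

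| Worsened days of 28 | Share of days | Share of readings | Overstatement of loss |
|---|---|---|---|
| 5 | 17.9% | 33.7% | 88% |
| 7 | 25.0% | 43.8% | 75% |
| 10 | 35.7% | 56.5% | 58% |
| 14 | 50.0% | 70.0% | 40% |

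For 7 days: 28 / (7 + 21 × 3/7) = 28/16 = 1.75. With a 30-day month the ratios are 1.91, 1.78, 1.62 and 1.44. Trying every start day on a real Monday/Wednesday/Friday calendar (28 days) gives 87-100% for 5-day episodes, 75% for 7-day and 40% for 14-day.

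Outside that band: 1 day 123%, 3 days 104%, 21 days 17%, 28 days 0%.

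**Incomplete recording.** With q readings per worsened day, the share of readings is qw / (qw + (M − w) × 3/7). At q = 0.8 the overstatement is 62%, 53% and 30% for 5, 7 and 14 days. At q = 3/7 it is zero. Below 3/7, as when a hospital stay passes without readings, the loss is understated instead.

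**Absolute size.** D = 65 − 65/1.17 = 9.4 to 65 − 65/1.22 = 11.7 L/min; from 38 L/min the same step gives 5.5 to 6.9 L/min. The excess is D × (share of readings − share of days).

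| Worsened days of 28 | Excess at 65 L/min | Excess at 38 L/min |
|---|---|---|
| 5 | 1.5-1.9 | 0.9-1.1 |
| 7 | 1.8-2.2 | 1.0-1.3 |
| 10 | 2.0-2.4 | 1.1-1.4 |
| 14 | 1.9-2.3 | 1.1-1.4 |

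For 7 days at 65 L/min, the time-weighted loss is 2.4-2.9 L/min and a plain mean reports 4.1-5.1. With an assumed milder fall of 5 L/min the excess is about 0.8-1.0 L/min (5 × 0.158 to 5 × 0.207).

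**Check of the remedies.** With weight 7/3 per stable reading and 1 per daily reading, the worsened share becomes w / (w + (M − w) × 3/7 × 7/3) = w/M, so the expected overstatement is 0% at any duration. Using only the Monday/Wednesday/Friday readings is within about 2% of zero on average over start days and exactly zero for 7-, 14- and 21-day episodes. For a 5-day episode it runs from −7% to +40% depending on the start day.

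**The case against.** The documents fix none of the conditions behind the 40-90% band: the duration of worsening, full daily recording, or an unweighted mean. That stands, so the figure can only be given conditionally.

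The inpatient fall in PIFR is an awkward partner for complete home recording. The plan schedules no PIFR in hospital, section 5.1.4.2 defers measurement in several conditions, and nothing is imputed. The most severe months could therefore be under-sampled and the bias reversed. This also stands.

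The shift is small beside the device's 5 L/min repeatability and the pilot SDs of 10-13 L/min (section 1.3), and half the target sample uses Handihaler, where it is smallest. If, as an assumption, 30% of months in one group and 10% in another were worsened, the bias in their contrast would be about 0.2 × 0.9 to 0.2 × 2.4, or 0.2-0.5 L/min. That limits the importance of the point but does not remove it: random error shrinks when a month's readings are averaged, and this bias does not.

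A reader might infer that the CAT and mMRC associations are inflated by the same factor. The documents do not support that. Correlations do not scale with the outcome in this way, section 5.1.2 leaves the self-assessment period unspecified, and a patient who has recovered by the call could show a weaker association. The month average is also only one of the two permitted choices.

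**Conclusion.** The point holds in conditional form. Reading frequency depends on clinical state, and the plan averages by month without allowing for it. If PIFR falls with worsening and readings follow the schedule, a plain mean overstates the month's loss by about 40-90% for an assumed 5 to 14 worsened days, and by 0% to over 120% across all durations.

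The percentage applies to the loss from the stable level. A reader might take it as the error in the PIFR average or in a model coefficient, but it is neither: the average moves by roughly 1-2 L/min, and a coefficient for, say, GOLD stage also carries any difference in stable PIFR, which this mechanism does not inflate.

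Exploratory associations with factors linked to worsening can be distorted; the direction for CAT and mMRC is not established. The primary endpoint does not use monthly averages, so neither it nor N=120 is touched. The change is worth making because it is cheap and the bias is systematic, not because the study's main result depends on it.

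**What to change.** In section 6.3, define weekly and monthly PIFR averages as time-weighted means. Weight each reading by the days it represents, derived from the reading dates: about 7/3 for readings at Monday/Wednesday/Friday spacing and 1 for daily readings. Working from dates avoids needing a daily record of clinical state, which the notebook is not described as capturing. State how longer gaps such as hospital stays are handled, so that the weights do not in effect impute missed readings.

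Use these averages in the mixed models and, where the month average is chosen, in the CAT and mMRC associations. Report averages from the Monday/Wednesday/Friday readings alone as a sensitivity analysis. Keep all daily readings for the analyses around exacerbations.

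The cost is a short addition to the analysis text and some extra programming, with no new data. Weighted averages are slightly noisier, and the weekday-only version is notably noisier for short episodes.

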Disease related factors that could affect a patient's inspiratory ability include diaphragmatic dysfunction, air trapping, narrowing of the airways, and worsening respiratory symptoms such as during an exacerbation. (Broeder, Jansenns, Malmberg, Taube, Loh, Sharma). In COPD patients with air trapping, it was shown that in addition to a reduced forced residual capacity and decreased inspiratory capacity, the inspiratory flow was also reduced. (Taube) Decreased inspiratory flow has been shown when COPD patients are clinically stable ([name], Janssen, Mahler, Seheult) and during exacerbations requiring hospitalization. (Broeder, Loh, Sharma) Studies by Loh and Sharma found that impaired PIFR, below minimums for DPIs, occurred in a third or more of COPD patients with acute exacerbations requiring hospitalization. The study by Loh indicated patients with impaired PIFR were at a greater risk of all cause 90-day re-hospitalization, whereas this was not found in the study by Sharma. In the study by Loh, the PIFR was performed in patients while in a sitting position. (personal communication) The decrease in inspiratory flow and capacity apparently persists for some time after exacerbations. Broeder reported that PIFR, using the InCheck DIAL®, increased between 17% and 22% between hospital admission and 5 weeks later when patients were clinically stable in the outpatient setting. There are no published studies that

have measured longitudinal changes in PIFR in ambulatory COPD patients when clinically stable and during periods of worsened respiratory symptoms and recovery.

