2 STUDY OBJECTIVES

2.1 Objectives:

- The primary objective of the study is to determine the proportion of patients with suboptimal peak inspiratory flow rate (sPIFR) measurements amongst COPD patients receiving dry powder inhaler(s) (DPI) in the ambulatory setting.
- The exploratory objectives are to characterize PIFR over time, the variability of PIFR measurements, and the associations with potential predictors (demographics, clinical, PRO, body position, device)
- Additionally, we will explore the exacerbations frequency and change in PIFR around period of exacerbation.

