3.3 Study Duration, Enrollment and Number of Subjects

Study duration and timeline: The duration of study is 24 weeks.

Enrollment: Participants will be recruited from UNC Clinics.

Number of subjects: One hundred twenty patients will be enrolled into this study.

Enrollment to ensure balance of seasonal effects across all arms: Enrollment such that the 24 week study period for each subject includes >2 months during the 'exacerbation season' of October – March (this translates into April and May being the only months to not enroll patients). Screening visits can be undertaken during these two months (April and May).

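### The mixed model for monthly PIFR names only a random subject effect, so standard errors for time effects are too small if patients' slopes differ or neighbouring months are correlated

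*Combined protocol and SAP*

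**What the plan says.** Section 6.3, under the exploratory analyses, states: "We will use mixed models to explore associations of monthly PIFR averages over time and clinical and demographic factors". The next sentence gives the structure: "Subjects will be considered as random factor, other variables will be considered fixed effects". Time is one of those other variables, so on the plain reading it is a fixed effect. Section 6.3 mentions no random slope, residual correlation structure or robust standard error. It does not say whether time is linear or categorical, or how two PIFR series from a patient on two dry powder inhalers enter the model.

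Three other places bear on the point:

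- Section 2.1 makes this a stated aim: "The exploratory objectives are to characterize PIFR over time, the variability of PIFR measurements".
- Section 6.3 sets the reading of p values: "All tests with p value < 0.05 will be interpreted nominally as statistically significant".
- Section 1.3 says of inspiratory flow: "The decrease in inspiratory flow and capacity apparently persists for some time after exacerbations". It cites a rise in PIFR of 17% to 22% over the 5 weeks after hospital admission.

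**The concern.** A random intercept absorbs differences in level between patients and nothing else. It treats a patient's monthly means, around that level and a common time trend, as independent readings. If patients drift at different rates, or a low month tends to be followed by another low month, those means carry less information about change than the model assumes. The standard error for change over time is then too small, the interval too narrow, and p<0.05 is reached too often by chance.

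The slow recovery described in section 1.3 can span adjacent monthly means, and section 1.3 also chose 24 weeks because 2 to 4 weeks was judged too short to show the full variability of PIFR. What is at stake is whether time trends, and any factor-by-time associations, reported under an exploratory objective can be taken at their nominal significance level.

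**Working it through.** **The plan's own figure.** The documents state no error rate, power or standard error for this model. The stated sample size rests on the primary proportion, and it reproduces: 1.96² × 0.40 × 0.60 / 0.088² = 119.06, rounded up to 120.

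**Inputs from the documents.** N = 120 (section 3.3); 24 weeks (section 3.3), taken as T = 6 four-week means; nominal level 0.05 (section 6.3), taken as two-sided; device repeatability 5 L/min for a single measurement (section 1.3).

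**Inputs not in the documents (assumed).** SD of patient slopes τ = 0.5 L/min per month; residual SD of a monthly mean σ = 2 to 3 L/min; lag-1 autocorrelation ρ = 0 to 0.5; balanced data with no missing months; one series per patient; linear time.

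**Formula.** With centred times −2.5 to 2.5, Sxx = 17.5. The true variance of the estimated slope is proportional to σ²A + τ²Sxx. The variance that a random-intercept model reports is, on the same scale, σ²B + τ²Sxx/5. Here A = t′Rt/Sxx and B = (T − 1′R1/T)/(T − 1), where R is the residual correlation matrix. For independent residuals A = B = 1. For ρ = 0.3, A = 1.287 and B = 0.869. For ρ = 0.5, A = 1.385 and B = 0.731. The false-positive rate is 2 × [1 − Φ(1.96/√ratio)].

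| τ | σ | ρ | Variance ratio | False-positive rate |
|---|---|---|---|---|
| 0 | any | 0 | 1.00 | 5.0% |
| 0.5 | 3 | 0 | (9 + 4.375)/(9 + 0.875) = 1.35 | 9.2% |
| 0.5 | 2 | 0 | (4 + 4.375)/(4 + 0.875) = 1.72 | 13.5% |
| 0 | any | 0.3 | 1.287/0.869 = 1.48 | 10.7% |
| 0 | any | 0.5 | 1.385/0.731 = 1.89 | 15.4% |
| 0.5 | 3 | 0.5 | (12.46 + 4.375)/(6.58 + 0.875) = 2.26 | 19.2% |
| 0.5 | 2 | 0.5 | (5.54 + 4.375)/(2.925 + 0.875) = 2.61 | 22.5% |

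**Check by simulation** (120 patients, 6 months, 20,000 datasets per scenario). With σ = 3, τ = 0.6 and 1.1 gave 11.0% and 20.0%; ρ = 0.3 and 0.6 gave 10.6% and 18.0%. A test based on each patient's own slope gave 4.7% to 5.3% throughout. For a two-group-by-time term at τ = 0.5, simulation gave 9% to 15%. Direct REML random-intercept fits to 189 to 300 datasets in each of three scenarios rejected in 13%, 23% and 18%, and each decision agreed with the closed-form test.

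**Where the effect is small or absent.**

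- Omnibus test of categorical month: 5.5% and 7.0% at τ/σ = 0.2 and 0.38, and 13% at the extreme value 2.
- A single contrast of month 6 with month 1: 8.8% and 15.1% at τ/σ = 0.2 and 0.38.
- Main effect of a patient-level factor: 4.4% to 5.2% in every scenario simulated.
- Exacerbation dips alone (20%, recovering over 5 weeks, 0.5 to 1.5 per patient assumed): about 6% to 9% for linear time.

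**Where the direction reverses.** Suppose 40% of patients use two inhalers, with a device-specific patient SD of 8 L/min (both assumed) and σ = 3. If both series enter one model with only a subject effect and a fixed device term, the false-positive rate is 0.04% at τ = 0, 1.5% at τ = 0.6, 8.1% at τ = 1.1 and 24% at τ = 2. The patient-by-device variance falls into the residual and enlarges the standard error.

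**The case against.** The strongest reply is that the sentence names the grouping unit and does not literally exclude a subject-level random slope or a residual correlation structure. That stands in part: a fuller model could be fitted without contradicting the naming of subject as random. But the same sentence makes the other variables fixed, and nothing else in 6.3 points to a fuller model, so a random intercept is what an analyst would normally program.

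A reader might go further and infer that the standard errors are certainly too small and that false time effects will be two to four times too frequent. The documents do not support that. They give none of the three quantities that set the size. For linear time the possible range from slope variation runs from 1 to 7.6 times nominal (5% to 38%), and the direction can reverse when two device series share one subject effect. The recovery cited in section 1.3 follows hospital admission; it makes correlation between adjacent months plausible but does not establish an autocorrelation of 0.5, or differing 24-week slopes, in all outpatients. The pilot data show a stable mean PIFR over 2 to 4 weeks, though the protocol itself calls that period too short.

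It is also true that the analysis is exploratory with nominal p values, that section 6.2 lists no slope or mean-change endpoint, that no factor-by-time term is explicitly planned, and that 6.3 already describes PIFR over time for each patient and device. These points limit the consequence. They do not make the stated model a good one for change over time.

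**Conclusion.** The point holds in conditional form. As written, inference on a linear time trend or a factor-by-time term is valid only if patients share a slope and all months within a patient are equally correlated. Under the assumed values, false positives run at about 9% to 23% instead of 5%, and the reported standard error is 62% to 86% of the true one (1/√2.61 to 1/√1.35). If neither departure is present, there is no inflation. Main effects of patient-level factors are sound, and an omnibus month test is little affected. If two device series are pooled under one subject effect, the error can be in the conservative direction.

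These figures rest on assumed slope SD, autocorrelation and residual SD, and on balanced data. This is a minor-to-moderate improvement to an exploratory analysis. The primary proportion does not use this model, and N=120 does not depend on it.

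**What to change.** In section 6.3, before analysis:

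1. State how time is coded (linear or categorical month).
2. Fit each device separately, or add a patient-by-device random effect.
3. Use patient-clustered robust standard errors. Alternatively, fit a random intercept and a random time slope per patient-device series, falling back to robust standard errors if that model does not converge.
4. Report the between-patient slope SD and the within-patient SD, which also serves the variability objective in section 2.1.

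The cost is a sentence or two of text and somewhat wider intervals for time effects. If slopes prove equal and residuals independent, little is lost: the own-slope test kept a 4.7% false-positive rate in that case. A random slope combined with autoregressive residuals may be weakly identified from six means per patient, which is why robust standard errors are the simpler default. No change to sample size or data collection is needed.
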